## 9.10 Continuous temperature monitoring

A skin sensor temperature monitoring device with data logger will be issued to the parent/legal guardian for use in the first 24 hours following the 2, 4 and 12 months vaccinations (V1, V3 and V6). Parents will be given instructions in how to fit the temperature-monitoring device and how to check it remains in place, and what to do with the device at the end of the monitoring period. If the device fails or is not tolerated, the child will remain enrolled in the study and any data already collected will be used for descriptive analysis. If no continuous data is generated, the axillary temperatures alone will be analysed. Temperature monitoring devices can be collected either by a

member of a study team if the next visit occurs within 7 days and/or the device can be returned via post by the parents, using pre-paid envelops provided by the study team. The rational for using this system in this study, is based on previous studies that have shown that intermittent temperature measurements recorded less episodes of fever when compared with the continuous temperature monitoring.

#### 9.11 Potential risks for participants and mitigation strategies

1) **Immunisation schedule:** In this study we will be changing the times of the primary immunisations, for a different schedule when compared with the UK routine schedule. Currently the UK primary immunisation schedule is at 2, 3 and 4 months of age, and in this study it will be at 2 and 4 months. This schedule change, only affects the timing of administration for a few of the immunisations, **but the number of total doses administered will not change**. The pertussis vaccine, will be discussed separately in the next section.

The vaccines that would have variations from the routine schedule are:

- Rotavirus vaccine (rotarix®): currently given in the UK at 2 and 3 months of age. In our study it would be given at 2 and 4 months of age. This schedule remains in the recommended timelines [58], i.e. the first dose provided after 6 weeks of age and last dose before 6 months of age. The study schedule is similar to other European countries and we do not anticipate that this alteration would have any negative impact on the study population.

- Meningitis B vaccine (Bexsero®): This vaccine is going to be administered at the recommended ages according to the UK routine schedule (2 and 4 months). A small variation compared with the routine procedures will occur. The vaccine will be given separately at 7-14 days after the 2 and 4 month immunisations. The main reason for this slight variation is that the Meningitis B vaccine is considered very reactogenic and in order to better assess possible side effects/reactogenecity of the study vaccine, we think it is preferable to separate the administration of those 2 vaccines. We do not anticipate that this change would have any negative impact since children are normally vaccinated in the routine schedule in a time frame of 2 weeks, from the first day that they are eligible.

- Pneumococcal vaccine, PCV (Prevenar13®): the UK schedule is changing during early 2020 from that used in the current study, 2 and 4 months and booster at 12 months (2+1) to a single dose of PCV to be given at 3 months followed by the booster dose at 12 months (1+1 schedule). Given this is the first 1+1 schedule to be used globally and the current study has no visits at 3 months the

current study will keep a 2+1 PCV schedule. There is not thought to be a significant difference in the protection from pneumococcal disease in UK infants using either schedule and the two dose schedule will have the benefit of avoiding an extra visit at 3 months of age.

**2) Pertussis vaccines:** In this study, the main focus is going to be the pertussis vaccine that would be administered in two different formulations:

- aP group would receive the DTaP-IPV-Hib- Hep B (Infanrix hexa ®), a licensed vaccine in Europe. This vaccine was introduced into the UK routine schedule for babies born from 1st of August 2017, replacing the previous vaccine, a similar formulation that didn't contain the hepatitis B vaccine. Since the vaccine is the same as the current vaccine on the schedule, we do not anticipated any differences in side effects or any increased risk. This vaccine will also be the booster vaccine (12 months) for both control and test groups.

-wP group: The participants will receive the DTwP- Hib-Hep B (Comvac 5 ®) + Imovax ® polio at 2 and 4 months of age. The Imovax ® polio is licensed in Europe and Comvac 5® has manufacturing approval in India. Whole cell pertussis vaccines are given routinely in low and middle income countries throughout the world, and were in use in the UK until 2004. In general wP vaccines are more reactogenic than acellular vaccines, in terms of fever, irritability, and local reactions, although the symptoms are normally short lived and more common after booster doses. Other side effects, such as hypotonic hyporesponsive episodes, although rare are considered to occur at higher frequency (see Introduction: Adverse events after pertussis immunisation – aP and wP). In keeping with UK practice for MenB vaccines, which are considered relatively reactogenic, prophylactic paracetamol will be suggested for those infants given wP. This will follow the recommendation of the the UK department of health guidance for MenB given in the "Green Book" chapter on meningococcal disease (https://www.gov.uk/government/collections/immunisationagainst-infectious-disease-the-green-book). "A 2.5ml dose of liquid paracetamol (infant paracetamol 120mg/5ml) should be given orally as soon as possible after vaccination, followed by a second 2.5 ml dose after 4-6 hours and a third 2.5 ml dose 4-6 hours after the second dose. Should fever persist following the third dose and provided that the child appears otherwise well, additional doses of paracetamol may be administered at intervals of four to six hours for up to 48 hours. Parents should be advised to seek medical advice if their child is noticeably unwell with a fever present, or if the fever occurs at other times"

This vaccine has thimerosal in the composition as many of the other current vaccines. Thimerosal is used in vaccines as a preservative because of its anti-fungal and anti-septic properties. US Food and Drug administration (FDA) reported that approved vaccines that contain thimerosal as a

preservative have been proven to be safe under the regulatory requirements of this entity and the same position on safety was announced by the WHO and CDC. Although ComVac5 is not on the list of FDA approved vaccines, the amount of thimerosal and, consequently, mercury is similar to the vaccines listed (0.029 mg/0.5 ml of thimerosal; 29µg/0.5ml of mercury). WHO recommend the whole cell vaccines as the preferred vaccine for protection against Bordetella pertussis and it is used in the majority of the infants globally

All the adverse events are going to be recorded and evaluated by the DSMC.

**3) Pertussis vaccines schedule:** In our study the above described vaccines are going to be administrated at 2, 4 and 12 months of age (2+1). The rational for this change was that a minimum of two doses are required for protection according to WHO. The 2+1 schedule is part of NIP's in several European countries, especially Nordic, including Finland. If this schedule is performed at 2, 4 and 12 months, it is considered to combine the advantages of early protection in the most vulnerable age group with the advantages of a booster, when compared with the 3+0 schedules.. Although the 1st immunisation at 2 months of age might not induce antibody levels that would confer high level of protection in this population before the 2nd immunisation at 4 months of age, the infants will be already protected due to passive immunisation through their mothers. Since 2012, the UK Department of Health did the first recommendation to immunise all pregnant women with the pertussis vaccine since previous studies using tetanus, diphtheria and aP-containing (TdaP) combination vaccines during pregnancy have shown to reduce pertussis-related infant mortality and morbidity. All the infants recruited, would have this protection since it is an inclusion criterion for the study. Based on all this information and in the herd immunity, we do not believe that we are increasing any risk to the study population

**4) Blood samples**: All the children will need to have blood taken as part of the study. We do not anticipate any main issues with this procedure, since all the maximum volumes were calculated according to the NIHR Medicines for Children Research Network guidelines, and all the study staff carrying out the procedure are trained to do so. One of the main side effects is the risk of bruising after the procedure, which is normally not associated to any sequelae and short lived.

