#### 9.5.7 Visit 7: 28 days post V6 (+14 days)

#### Applicable for all sub-groups

1. Check Inclusion/ exclusion criteria are still valid

2. Review eDiary or paper diary for AEs/SAEs and prescription medicine since the last visit

3. Record and report any AEs/SAEs that have occurred since the last visit.

- 4. Measure and record axillary temperature
- 5. Blood sampling: obtain up to 6 mls

6. Collect Mucosal Lining Fluid (MLF) using synthetic absorptive matrices (SAM)

7. Administer 0.5ml MMR by intra-muscular injection into the upper right antero-lateral thigh record in source document and in red book

8. Administer 0.5ml Men C by intra-muscular injection into the lower right antero-lateral thigh record in source document and in red book.

9. Administer 0.5ml dose of 4CMenB by intra-muscular injection into the left antero-lateral thigh record site and time of vaccinations and batch number in source document and in red book

10. Observe the participant for 15 minutes after vaccination for any significant acute reactions, with appropriate medical treatment readily available in case of anaphylactic reaction. Any AEs occurring during the observation period should be recorded in the source document

11. Instruct parent/legal guardians to contact the study team immediately should they manifest any signs/ symptoms they perceive as serious or if the child is admitted to the hospital.

12. Complete paperwork in case of no direct data entry and enter onto database

13. Give letter of "end of the study" to the parents

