- **Men B:** Bexsero® (Novartis): a meningococcal serogroup B vaccine adsorbed rDNA vaccine. This vaccine is licensed in Europe and currently given as part of the UK routine schedule (2, 4 and 12 months).
- Men C: Neisvac-C ® (Pfizer Ltd): Meningococcal Group C Polysaccharide Conjugated Vaccine adsorbed. Is recommended for active immunisation in children from 2 months of age, adolescents and adults for prevention of the *Neisseria meningitidis* serogroup C disease and is licensed in Europe. MenC is currently part of the UK immunization schedule at 12 months of age (Menitorix: MenC and Hib combined vaccine). We intend to administer the monovalent MenC vaccine (Neisvac-C ®) because the Hib component is contained in infanrix-hexa.
- Rotavirus: Rotarix® (GSK): a live attenuated vaccine (RIX4414 strain) that is administered orally as a suspension in a pre-filled oral applicator. It protects against gastroenteritis caused by rotavirus. This vaccine is licensed and is part of UK routine schedule at 2 and 3 months. This vaccine is only going to be administered at 2 and 4 months of age

MMR: Priorix® (GSK): a live attenuated vaccine that protects against measles (Schwarz strain), mumps (RIT 4385 strain) and rubella (Wistar RA 27/3 strain) or M-M-RVAXPRO® (Merck,Sharp and Dohme) UK. Is indicated for active immunisation in children more than 9 months of age, adolescents and adults, to prevent the diseases above described. This vaccine is licensed in Europe and is given in the UK as part of the routine schedule at 12 months and 3 ½ years of age. This vaccine is going to be administered in UK at 13 months of age

Where needles are not supplied with the vaccine a 25mm, 23 gauge (0.6mm) needle will be used.

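### Section 9.11 says total doses are unchanged, but every infant in both arms gets 3 Hib doses against the UK routine 4, and the protocol does not disclose it

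*Protocol*

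**What the plan says.** Section 9.11, item 1, sets out the departure from routine. It describes UK practice as follows: "Currently the UK primary immunisation schedule is at 2, 3 and 4 months of age". The trial uses 2 and 4 months instead. The protocol says this affects timing for a few vaccines, "but the number of total doses administered will not change". It defers pertussis to a later item and then lists the vaccines that vary from routine: rotavirus, MenB and PCV. Neither Hib nor MenC is in that list.

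The Hib content has to be pieced together from other places:

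- Section 9.11, item 2, says of the hexavalent (Hib-containing) vaccine: "This vaccine was introduced into the UK routine schedule for babies born from 1st of August 2017". Section 13.2.2 describes the UK primary schedule as 3+0.
- Section 10.1, Men C, says: "MenC is currently part of the UK immunization schedule at 12 months of age (Menitorix: MenC and Hib combined vaccine". The trial departs from this: "We intend to administer the monovalent MenC vaccine (Neisvac-C ®) because the Hib component is contained in infanrix-hexa".
- Table 1 (section 7.2) and section 10.1 give the aP arm the hexavalent vaccine at 2, 4 and 12 months. The wP arm gets pentavalent Comvac 5, which also contains Hib, at 2 and 4 months and the hexavalent vaccine at 12 months.

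Section 9.11, item 3, on the pertussis schedule, concludes: "we do not believe that we are increasing any risk to the study population".

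**The concern.** Two changes act together on Hib. The third hexavalent dose moves from the primary course to 12 months, so it takes the place of the dropped 3-month dose. The 12-month MenC/Hib vaccine is then replaced by MenC alone, on the ground that the hexavalent vaccine already contains Hib. One hexavalent dose at 12 months cannot make up for both losses.

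The risk section therefore credits the schedule with a property it lacks. An ethics committee, a parent or a GP reading it would take it that no dose is lost. Item 3 does not fill the gap. It rests on a two-dose minimum for pertussis, on maternal vaccination and on herd immunity, and the maternal vaccine is diphtheria, tetanus and acellular pertussis with no Hib component. What is at stake is accurate disclosure and a correct vaccination record, not the trial's comparison.

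**Working it through.** The check is a dose count per antigen, using only products and ages that the protocol names (sections 7.2, 9.11, 10.1 and 13.2.2).

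**The plan's own figure.** The stated change in total doses is 0. It is reproduced for most antigens (UK / aP / wP):

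- Diphtheria, tetanus, pertussis, HepB: 3 / 3 / 3.
- Polio: 3 / 3 / 3 (wP arm: 2 stand-alone IPV + 1 hexavalent).
- Rotavirus 2 / 2 / 2; MenB 3 / 3 / 3; MenC 1 / 1 / 1; MMR to 13 months 1 / 1 / 1.
- PCV: 3 / 3 / 3 against the older UK schedule. After the 2020 change to 1+1 the UK figure is 2. Section 9.11 discloses that change.

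**Hib.**

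| Dose | UK routine | aP arm | wP arm |
|---|---|---|---|
| 2 months | hexavalent, 1 | hexavalent, 1 | pentavalent, 1 |
| 3 months | hexavalent, 1 | 0 | 0 |
| 4 months | hexavalent, 1 | hexavalent, 1 | pentavalent, 1 |
| 12 months, hexavalent | 0 | 1 | 1 |
| MenC dose (UK 12 months, trial 13 months) | MenC/Hib, 1 | MenC only, 0 | MenC only, 0 |
| **Total Hib** | **4** | **3** | **3** |

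Change = 3 − 4 = −1 dose per infant in each arm; 3/4 = 0.75, so 25% fewer. From 4 to 12 months (12 − 4 = 8 months) infants hold 2 doses instead of 3; 2/3 = 0.67, so a third fewer. Hib is the only antigen that falls.

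**Alternative reading: doses as products given.**

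- UK: 3 hexavalent + 2 rotavirus + 3 PCV + 3 MenB + 1 MenC/Hib + 1 MMR = 13 (12 with PCV as 1+1).
- aP: 3 hexavalent + 2 rotavirus + 3 PCV + 3 MenB + 1 MenC + 1 MMR = 13.
- wP: 2 pentavalent + 2 IPV + 1 hexavalent + 2 rotavirus + 3 PCV + 3 MenB + 1 MenC + 1 MMR = 15.

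This matches in the aP arm against the older PCV schedule, but not in the wP arm.

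**The case against.** **Scope of the sentence.** It describes one change, from three primary visits to two, and pertussis is set aside for separate treatment. Hib travels in the pertussis combination, whose doses number 3 against 3. This reading has some force, but the later pertussis items never mention the Hib count, and counting by product fails for the wP arm.

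**A deliberate choice.** Section 10.1 gives a reason for MenC alone: Hib is in the hexavalent vaccine, given 28 to 42 days before Visit 7. A reader might infer that the product choice rests on a miscount. The documents do not support that. The stated reason fits a decision not to repeat Hib within weeks, and no tally is cited. What is missing is disclosure.

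**Safety capture.** Section 13.2.2 names confirmed pertussis as an SAE because of the reduced schedule and does not name Hib. A reader might infer that Hib disease would go unreported. It would not: a hospitalised, life-threatening or medically important case is an SAE under the general criteria, and section 13.3.2 requires all SAEs from consent to last visit to be reported.

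**Justification of 2+1.** For Infanrix hexa, section 10.1 already ties the schedule to the SmPC. For Comvac 5, the background section mentions a 3-dose primary course, but as the design of a 2007 comparator trial. Dosing detail sits in the IB and IMPD, which are not shown, so two doses cannot be called off-label from this document.

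**Serology.** Hib antibody is measured at 2, 5, 12 and 13 months (secondary endpoint 6). That stands, but an aP v wP comparison cannot show a shortfall shared by both arms.

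**Conclusion.** The concern holds as an incorrect statement in the risk section and an undisclosed reduction: 3 Hib doses instead of 4 in both arms. The count assumes the UK schedule is as the protocol describes it, with the hexavalent vaccine at all three primary visits, and that doses are counted per antigen.

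The severity is minor. The count is the same in both arms, so endpoints, the aP v wP comparisons and power are unaffected. A reader might infer that infants are left less protected. The document gives no Hib incidence and does not say that three doses protect less than four, so no harm is shown and no absolute risk can be computed.

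**What to change.** 1. In 9.11, item 1, say that total doses are unchanged except for Hib (3 instead of 4) and for PCV as described below it.
2. Add Hib/MenC to the list of variations, with a short reason for accepting 2+1 Hib: the SmPC for Infanrix hexa and the IB for Comvac 5.
3. Cross-refer to this from the Men C entry in 10.1.
4. In the notification to the GP and child health department that section 9.2 already provides for, state that the infant has had 3 Hib doses, not the routine 4.

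The cost is a few sentences and one line in an existing letter. There is no extra visit, sample or analysis. For infants already past Visit 7, the text correction and notification are all that apply; the document does not show how many visits remain.

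Giving MenC/Hib at Visit 7 is an optional clinical choice for the sponsor. It would bring the total to 3 + 1 = 4 without adding an injection. It would not disturb the 13-month samples, because in section 9.5.7 sampling ("Blood sampling: obtain up to 6 mls", step 5) comes before the vaccines ("Administer 0.5ml Men C by intra-muscular injection into the lower right antero-lateral thigh", step 8). It would need supply, an amendment and a view on repeating Hib after 28 to 42 days, and it would leave the 2 v 3 difference from 4 to 12 months as it is. A separate Hib SAE rule is not needed.

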	5. To compare other pertussis specific antibody responses including FHA, PRN- and FIM specific antibodies in infants primed with aP versus wP	5.FHA, PRN and FIM specific antibody GMCs prior to immunisation and at 2, 5, 12 and 13 months of age

6. To compare serological responses to the non-pertussis vaccines (Hib, diphtheria, tetanus, pneumococcus) in infants primed with aP versus wP vaccines	6.Hib, diphtheria, tetanus, and pneumococcal-specific antibody responses at 2, 5, 12 and 13 months in the aP versus wP groups
7. Assessment of pertussis specific functional antibodies prior to and after immunisation with aP versus wP vaccines	7.Assays of pertussis specific functional antibodies may include: adherence inhibition; bacterial agglutination; bactericidal activity; bacterial opsonization and phagocytosis undertaken on serum or plasma samples taken at 2 (prior to immunisation), 5, 12 and 13 months of age
8. To determine the induction and persistence of mucosal antibodies and/or cytokines in mucosal lining fluid before vaccination (2 months) and after vaccination (at 5 and 12 months)	8. The soluble factors in the eluate from nasosorption will be analysed by Luminex multiplex immunoassay
9. To assess vaccine reactogenicity in those primed with aP versus wP vaccines	9. Proportion of individuals with local and systemic symptoms (solicited and unsolicited) after vaccine doses at 2, 4 and 12 months in infants primed with aP versus wP vaccine.

Exploratory	1. Assessment of pertussis specific	1.Exploratory T-cell assays
	T-cell responses to aP versus wP	(including, but not limited to
	vaccination	measurement of intra-cellular
		and supernatant cytokines from
		ex-vivo stimulated PBMCs) to
		assess T-cell responses at a
		variety of time-points around
		dose 1 (baseline), 5, 12 and 13
		months.
	2. Assessment of genetic and	2. Measurement of genetic
	epigenetic determinants of the	variation (e.g. SNPs in candidate
	immune response to aP or wP	genes, B-cell repertoire in bulk
	immunisation	and individual B-cells) and
		epigenetic variation (e.g.
		methylation and histone
		modification) and correlation
		with vaccine immunogenicity
		and reactogenicity
	3. To assess vaccine reactogenicity	3. Continuous body temperature
	in those primed with aP versus wP	measurements in the first 24
	vaccines using novel methods	hours after the administration of
		the study vaccines
	4. To explore parental motivations	4. Parent motivation and

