#### Then:

1.Administer 0.5ml DTaP-IPV-Hib-Hep B by intra-muscular injection into the upper right anterolateral thigh (aP group) record in source document and in red book

2. Administer 0.5ml DTwP-Hib-Hep B by intra-muscular injection into the upper right antero-lateral thigh (wP group), record in source document and in red book

3. Administer 0.5ml PCV by intra-muscular injection into the upper left antero-lateral thigh record in source document and in red book (both aP and wP groups)

4. Administer 0.5ml IPV by intra-muscular injection into the lower left antero-lateral thigh (wP group), record in source document and in red book

5. Administer Rotavirus vaccine oral drops

6. Issue eDiary login details to parent (or give paper diary), ask parent to login and change password. Demonstrate eDiary (or paper diary) to parents for recording AEs and paracetamol +/-ibuprofen use and check understanding.

7. Issue a digital thermometer and ruler. Explain how to measure and record temperature, local and systemic reactions, AEs (for 7 days post any vaccination) and concomitant medications (for 28 days post vaccination).

8. Issue the parents/ legal guardian with a continuous temperature-monitoring device together with instructions. Fit on the child and demonstrate how to fit, check function and remove device

9. Observe the participant for 15 minutes (or for 30 minutes for participants who have received Comvac5) after vaccination for any significant acute reactions, with appropriate medical treatment readily available in case of anaphylactic reaction. Any AEs occurring during the observation period should be recorded in the source document

10.Issue (only if parent's do not have any) and provide instructions on the use of paracetamol prophylaxis to those whose infant is randomised to receive wP

11. Instruct parent/legal guardians to contact the study team immediately should the infant manifest any signs/ symptoms they perceive as serious or if the infant is admitted to the hospital.

12. Leave with parents/guardians anaesthetic cream (unless spray is to be used), dressing pads and instructions for blood test visit (V5, at 5months).

13. Schedule next visit

14. Study staff complete red book, paperwork in case of no direct data entry and enter onto database

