## 13.3 Adverse events, serious adverse events and suspected unexpected serious adverse reactions: Procedures

#### 13.3.1. Procedures for Recording Adverse Events:

For the first 7 days after immunisation at visits 1, 3 and 6 (Day 0 to Day 7), all AEs observed by the study team or reported by the participant's parent/ legal guardian, whether or not attributed to study medication, will be recorded in the RedCap or paper diary. Reactions occurring in the first 7 days after immunisation (including day of immunisation) will be divided up into: solicited reactions, which will be considered related to study vaccine unless stated otherwise; and unsolicited adverse events, which will be assessed for relatedness and graded for severity by a medically qualified member of the study team. There will be space in the electronic or paper diary to record the end date of adverse events that continue beyond Day 7. The RedCap system will allow review by clinical staff of grade 3 AEs in real-time.

Medical events not considered SAEs that occur 7 days after immunisation do not need to be recorded. Because of the possibility that medication may interfere with the evolution of an immune response, the details of any prescription medication that is given within 28 days following the 2, 4 or 12 month vaccinations will be recorded on the eDiary or paper diary. Information on paracetamol/ ibuprofen use within 72 hours prior to immunisation and in the 7 days following immunisation will be specifically asked for.

AEs will be recorded using the following guidance:

• Pre-existing medical conditions (present before start of the AE collection period) are considered "concurrent medical conditions" and should not be recorded as AEs. However, if the participant experiences a worsening or complication of such a condition, the

worsening or complication should be recorded as an AE. Investigators should ensure that the AE term recorded captures the change in the condition (e.g. "worsening of")

 Each AE should be recorded to represent a single diagnosis. Accompanying signs or symptoms (including abnormal laboratory values) should not be recorded as additional AEs.

All AEs that are considered related and result in a participant's withdrawal from the study or are present at the end of the study should be followed up until the end of symptoms or the condition becomes stable.

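### At the 2- and 4-month doses paracetamol prophylaxis is suggested only for wP infants, so the reactogenicity and 24-hour temperature results compare strategies, not the vaccines alone as the objectives are worded

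*Protocol*

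**What the plan says.** **Who gets the advice.** Protocol section 9.11, item 2, states that "prophylactic paracetamol will be suggested for those infants given wP". Section 9.5.1 (Visit 1, vaccination list, step 10) tells staff to "provide instructions on the use of paracetamol prophylaxis to those whose infant is randomised to receive wP"; section 9.5.3 (Visit 3, step 14) repeats the instruction. Neither visit has a matching step for aP infants.

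**Timing.** Section 9.11 quotes guidance for a prompt first dose, with the rest of the course described as "followed by a second 2.5 ml dose after 4-6 hours and a third 2.5 ml dose 4-6 hours after the second dose". If fever persists after the third dose and the child otherwise appears well, "additional doses of paracetamol may be administered at intervals of four to six hours for up to 48 hours".

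**What is measured.** Secondary objective 9 (Synopsis and section 6) is "To assess vaccine reactogenicity in those primed with aP versus wP vaccines". Its endpoint is "Proportion of individuals with local and systemic symptoms (solicited and unsolicited) after vaccine doses at 2, 4 and 12 months". Exploratory objective 3 addresses the same question with continuous temperature. Section 9.10 issues the sensor "for use in the first 24 hours following the 2, 4 and 12 months vaccinations", and section 9.8 sets a 7-day symptom diary after the same vaccinations.

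**Analysis.** Section 14.1 analyses reactogenicity by primary schedule and by vaccine dose, and does not mention the arm-specific advice. Section 9.9 records paracetamol and ibuprofen use in both arms, from 72 hours before to 7 days after these vaccinations.

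**The concern.** The objectives ask how reactogenic the two vaccines are. At 2 and 4 months, vaccine and antipyretic advice coincide completely by arm: every wP family receives the advice and no aP family does. The protocol expects more fever, irritability and local reactions after wP (section 9.11). An antipyretic suggested to that arm would be expected to hide some of these, fever above all.

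At stake is what the trial may conclude. Followed as written, a small or null difference at the priming doses would be reported as a property of the vaccines when it could be partly or wholly the effect of the paracetamol. The protocol does care about a clean reading here: section 9.11 moves the MenB vaccine 7 to 14 days away so that reactions to the study vaccine can be assessed better. It does not acknowledge the difference that the paracetamol advice creates.

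**Working it through.** **1. Dose by dose**

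| Vaccination | Pertussis vaccine, aP arm / wP arm | Paracetamol advice in the protocol |
|---|---|---|
| Visit 1, 2 months (9.5.1) | aP / wP | wP arm only |
| Visit 3, 4 months (9.5.3) | aP / wP | wP arm only |
| Visit 6, 12 months (9.5.6) | aP / aP | none specific to an arm |

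The MenB visits (9.5.2 and 9.5.4) carry paracetamol advice for both arms, 7 to 14 days after priming, so they create no difference between arms. The advice differs at exactly the two doses where the pertussis vaccines differ.

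**2. Overlap with the measurement windows**

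The suggested doses fall at 0 h, at 4–6 h, and at (4–6) + (4–6) = 8–12 h. All three lie inside the 24-hour temperature recording and the 7-day diary. Assuming that each dose acts for 4–6 h (not stated in the protocol), the three reach to between 8 + 4 = 12 h and 12 + 6 = 18 h. That is 12/24 = 50% to 18/24 = 75% of the recording.

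**3. Direction**

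Let p_w and p_a be the fever proportions without antipyretic, u_w and u_a the proportions of infants given it, and RR its relative risk for fever, taken as equal in both arms. Then:

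- observed difference = p_w × [1 − u_w(1 − RR)] − p_a × [1 − u_a(1 − RR)]
- difference lost = (1 − RR) × (p_w × u_w − p_a × u_a)

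With RR below 1, p_w at least p_a (the protocol's expectation) and u_w above u_a (the purpose of the advice), the loss is positive. The observed wP excess is therefore smaller than the excess without antipyretic.

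**4. Size**

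The protocol gives no fever rates, uptake or effect of paracetamol. The following inputs are all assumptions and show only how far the answer moves. Take p_w = 0.50, p_a = 0.20 and u_a = 0, so the difference without antipyretic is 30 points.

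| u_w | RR | Observed wP | Observed difference |
|---|---|---|---|
| 0.50 | 0.75 | 0.50 × 0.875 = 0.4375 | about 24 points |
| 0.75 | 0.50 | 0.50 × 0.625 = 0.3125 | about 11 points |
| 1.00 | 0.50 | 0.50 × 0.50 = 0.25 | 5 points |

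The range is wide because uptake and effect are unknown. Any use in the aP arm would reduce the loss.

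**5. The protocol's own figure**

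No power or margin is stated for reactogenicity. The only power figure, 90.8%, is for the PT comparison in section 7.1.2. It reproduces as 90.83% (two-sided t-test, 45 per arm, SD 0.324, difference log10(135/80) = 0.227). This point does not depend on it.

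**6. Can an analysis separate the two effects?**

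Not from this design. No wP group goes without the advice. Recorded use arises after randomisation and may be prompted by symptoms, so comparing users with non-users would not recover the vaccine effect.

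**The case against.** Allocation is randomised, so the contrast is valid for the two strategies as delivered. Objective 9 makes no explicit promise of an antipyretic-free effect, and the protocol makes no equivalence or tolerability claim. Paracetamol is only suggested in the wP arm and is not barred in the aP arm. Doses beyond the third apply only if fever persists, so they follow an event that could already have been recorded; axillary readings are scheduled during the first day and whenever a parent suspects fever. The diary also covers symptoms on which paracetamol may have little bearing. Tabulating antipyretic use is ordinary SAP content.

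Most of this stands and limits the point to what the priming-dose comparison estimates. It does not remove it: the objectives are fixed in the protocol, they name the vaccines alone, and no SAP can undo the overlap.

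Three stronger readings are tempting, and the documents do not support them:

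- **The reactogenicity comparison is invalid or cannot answer its objective.** Randomisation protects the comparison of strategies, and an observed wP excess would still be informative.
- **The immunogenicity results are compromised too.** The clause in section 13.3.1, "Because of the possibility that medication may interfere with the evolution of an immune response", introduces the recording of prescription medication. Paracetamol and ibuprofen follow in a separate sentence with no reason given.
- **The 12-month dose offers a clean substitute.** It carries no arm-specific advice, but both arms then receive the same aP booster, so it does not compare wP with aP as vaccines.

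**Conclusion.** The point holds for the 2- and 4-month doses. There, endpoint 9 and the 24-hour temperature data estimate wP with suggested prophylactic paracetamol against aP without that advice, while the objectives and section 14.1 describe vaccine reactogenicity. The expected bias, relative to the vaccines' own reactogenicity, is towards no difference. This assumes that paracetamol lowers fever and that use is higher in the wP arm. An observed wP excess would remain evidence of greater wP reactogenicity, but neither its size nor a small or null difference would measure the vaccines' own profiles. The size of the masking cannot be determined from the protocol. The primary PT endpoint is outside this point, and no view is taken on whether paracetamol should be advised.

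**What to change.** Leave the clinical advice unchanged, and reconcile objective and endpoint 9, exploratory objective 3 and section 14 with sections 9.5.1, 9.5.3 and 9.11.

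1. State that at the 2- and 4-month doses the reactogenicity and temperature comparisons are of strategies: wP with suggested prophylactic paracetamol versus aP without that advice. The aP label should refer to the advice, since aP infants may also have been given paracetamol.
2. State that little or no difference at these doses will not be read as similar intrinsic reactogenicity.
3. Report the antipyretic use already recorded under section 9.9, by arm and vaccine dose, beside the reactogenicity and temperature results. Any split of infants by use should be labelled descriptive only.

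The cost is a few sentences and some tables from data already collected. No visit, procedure or sample size changes. The price is a narrower reactogenicity claim at the priming doses.
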